2.7.2.4.1 Time to event analysis for Recrudescence

Recrudescence is defined as appearance of asexual parasites after clearance of initial infection with a genotype identical to that of parasites present at baseline. Recrudescence must be confirmed by PCR analysis.

Incidence rates of recrudescence up to Day 29 will be estimated by the Kaplan-Meier method based on the subset of FAS patients who have clearance of initial infection by Day 7. Descriptive statistics (mean, standard error, median, quartiles) will be presented using the Kaplan-Meier method by treatment and cohort. Kaplan-Meier curves will be provided by treatment and cohort. For all cohorts pooled, difference for the cipargamin regimen vs artesunate will be evaluated using a log-rank test stratified by cohort (Cohorts 1 and 2 pooled as one cohort). Two-sided 90% CIs for the hazard ratio will be provided.

Time to event (recrudescence) will be calculated from the time of first study medication to the date of first event if a patient experience the event and be censored at the time of last parasite assessment if a patient does not experience the event. Reappearance of the parasites but with missing PCR data will be considered as censored at the time of reappearance of parasites.

2.7.2.4.2 Time to event analysis for reinfection

Reinfection is defined as appearance of asexual parasites after clearance of initial infection with a genotype different from those parasites present at baseline. Reinfection must be confirmed by PCR analysis.

Incidence rates of reinfection at Day 29 will be estimated by the Kaplan-Meier method based on the subset of FAS patients who have clearance of initial infection by Day 7. Descriptive statistics (mean, standard error, median, quartiles) will be presented using the Kaplan-Meier method by treatment and cohort. Kaplan-Meier curves will be provided by treatment and cohort. For all cohorts pooled, difference for the cipargamin regimen vs artesunate will be evaluated using a log-rank test stratified by cohort (Cohorts 1 and 2 pooled as one cohort). Two-sided 90% CIs for the hazard ratio will be provided.

Time to event (reinfection) will be calculated from the time of first study medication to the date of first event if a patient experiences the event and be censored at the time of last parasite assessment if a patient does not experience the event. Reappearance of the parasites but with missing PCR data will be considered as censored at the time of reappearance of parasites.

2.7.2.5 Analyses of secondary endpoints related to parasite clearance dynamics

The following analyses are described for the $\geq 90\%$ *P. falciparum* asexual parasite reduction, PRR and PCE slope half-life. The analysis will be based on FAS.

- Proportions of patients with $\geq 90\%$ *P. falciparum* asexual parasite reduction from baseline at 24 and 48 hours

For these two endpoints, data will be analyzed similar to the analysis of primary endpoint as specified in [section 2.5.2](#). Intercurrent events as well as missing data will also be handled similar to that of primary endpoint as specified in [section 2.5.3](#) and [section 2.5.4](#).

- *P. falciparum* asexual parasite reduction ratios (PRR) at 12, 24 and 48 hours

For each patient, the asexual PRR at a specific timepoint will be calculated as the ratio of asexual parasite at baseline divided by asexual parasite at that timepoint. If the asexual parasite count at a timepoint is 0/below assay detection limit, the detection limit will be used to calculate the ratio.

Descriptive statistics including median and geometric mean of asexual PRR at Hour 12, 24 and 48 will be provided by cohort and treatment group using the FAS. For each PRR, 2-sided 90% CIs for geometric mean for each treatment group and geometric mean ratio between each IV cipargamin regime vs IV artesunate by cohort will be provided using an analysis of covariance (ANCOVA) model on the log scale with log baseline value as a covariate and treatment group as a factor by assuming PRRs follow log normal distribution and transformed back using the exponential.

For all cohorts pooled, the analysis will be performed with cohort as an additional factor in the ANCOVA model. Observed data will be used.

- PCE slope half-life

Parasite clearance rate constant and slope half-life for parasite clearance will be calculated for each patient using the WWARN (World Wide Antimalarial Resistance Network)

Parasite Clearance Estimator as described in [Flegg et al. \(2011\)](#). The following are the key steps:

For each patient separately:

Step 1: Perform data cleaning. All further steps are performed on data with outliers, tails, extreme values and trailing zeros removed. For convenience of notation, if there is a zero parasitaemia that directly follows the last positive parasitaemia, it is replaced with the detection limit. This data point is subsequently counted as a non-zero parasite count.

Step 2: Perform checks to see if the clearance rate constant cannot be estimated:

(i) Number of non-zero parasite measurements (including a zero replaced with the detection limit) less than three

(ii) Initial parasitaemia too low: initial parasitaemia $< 1,000$ parasites per microliter

(iii) Final recorded parasitaemia too high: final parasitaemia $\geq 1,000$ parasites per microliter

(iv) A zero parasitaemia has been recorded, but the last positive parasitaemia is too high and the zero count is uninformative: last non-zero parasitaemia $\geq 1,000$ parasites per microliter

A zero parasitaemia is defined to be uninformative if the normal linear regression fitted to all the data points (excluding the zero count) gives a confidence interval for the time when the parasitaemia is below the level of detection which includes the time-point when the zero parasitaemia was recorded.

Step 3: Perform additional check to see if there are not enough data to estimate a lag phase (v) There are fewer than three measurements in the first 24 hours or a time difference between measurements in the first 24 hours is more than 14 hours

Step 4: Perform model fitting

- If none of the exclusion criteria (i)-(iv) in **Step 2** and (v) in **Step 3** are satisfied, fit polynomial models to the natural log-parasitaemia *versus* time data
- If none of the exclusion criteria (i)-(iv) in **Step 2** are satisfied but exclusion criterion (v) in **Step 3** is satisfied fit tobit linear regression if a zero parasitaemia has been recorded or linear regression otherwise.
- If one or more of the exclusion criteria are satisfied in **Step 2**, the clearance rate constant and duration of lag phase cannot be estimated.

Step 5: Estimate clearance rate constant (K) and duration of lag phase (t_{lag})

The above derivation will be performed using the PCE tool in R developed by WWARN. Descriptive statistics for parasite clearance rate constant and slope half-life for parasite clearance will be provided by cohort and treatment group using the FAS. 2-sided 90% CIs for each treatment group and for treatment ratio between each IV cipargamin regime vs IV artesunate by cohort will be provided using an analysis of covariance (ANCOVA) model on the log scale with log baseline value as a covariate and treatment group as a factor. For all cohorts pooled, the analysis will be performed with cohort as an additional factor in the ANCOVA model.

- Analysis of hospitalization data

Day of discharge from hospital will be summarized descriptively by cohort and treatment group. Number and percent of patients discharged on different days will be summarized. Day of death will be used in case of death during hospitalization. Time to discharge from hospitalization will also be analyzed using time to event analysis as described in [Section 2.7.2.4](#). Patients who do not discharge or die during study will be censored at the last assessment or at the time of death respectively.

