12.4.5 Sensitivity analyses for primary endpoint/estimand

After receiving antimalarial medication, a participant's parasite usually decreases log-linearly after a lag stage ([White 2011](#), [Flegg et al 2011](#)). For artemisinin derivatives, parasitemia starts to decline in a log-linear manner almost as soon as parasiticidal drug concentrations are reached ([White 2011](#)). The T_{max} is about 0.5 to 15 minutes for IV artesunate ([Artesunate PI](#)). The T_{max} is about 4 hours for oral cipargamin and should be much shorter for IV cipargamin. Missing data of parasite counts at 12 hours could be well estimated using a log linear interpolation of the 2 parasite counts immediate before and after 12 hours. Since there are 3 planned parasite assessments on or after 2 hours, missing parasite count at 12 hours due to early discontinuation could be estimated using participant specific log linear regression if there are at least 2 parasite counts prior to the discontinuation. A sensitivity analysis will be performed using interpolation for missing data at intermediate time points and extrapolation using a log linear regression if there are at least 2 parasite counts prior to discontinuation. In the event that a participant does not have at least 2 parasite counts prior to discontinuation, the participant will be imputed as not achieving $\geq 90\%$ reduction at 12 hours. Parasite counts below the limit of detection will be substituted using the half limit of detection.

The severity of disease is different between Cohort 1 and Cohort 2, which might impact the ability to achieve $\geq 90\%$ parasite reduction, ie., resulting in a different binomial distribution between Cohorts 1 and 2. Therefore, two-sided 90% confidence intervals (CI) for the difference between each IV cipargamin dose regimen vs IV artesunate will be provided for Cohort 1 and Cohort 2 separately, using handling of missing values not related to intercurrent events specified in [Section 12.4.4](#) and in this section.

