Analysis of secondary endpoints related to parasite clearance dynamics

All analyses will be performed using the FAS.

Proportions of participants with ≥ 90% *P. falciparum* asexual parasite reduction from baseline at 24 and 48 hours: missing data due to intercurrent and non-intercurrent events will be handled similar to the primary efficacy endpoint (See [Section 12.4.3](#), [Section 12.4.4](#)). These 2 variables will be analyzed using the statistical methods specified in [Section 12.4.2](#), [Section 12.4.5](#) and [Section 12.4.6](#).

PRRs at 12, 24 and 48 hours: PRR is defined as the ratio of asexual parasite at baseline divided by asexual parasite at post-baseline. If the asexual parasite count at post-baseline is 0, the half value of detection limit will be used to calculate the ratio. Missing values will not be imputed. For each PRR, 2-sided 90% CIs for each treatment group and for treatment ratio between each IV cipargamin regime vs IV artesunate by cohort will be provided using an analysis of covariance (ANCOVA) model on the log scale with log baseline value as a covariate and treatment group as a factor. For all cohorts pooled, the analysis will be performed with cohort as an additional factor in the ANCOVA model.

PCT and FCT: PCT will be calculated based on uncorrected *P. falciparum* asexual parasite counts. If a participant does not experience an event (such as *P. falciparum* parasite clearance, etc.), the time to the event will be censored at the last relevant assessment (such as last *P. falciparum* parasite assessment, etc.) participants who do not have the health condition at baseline (eg, fever, etc.) will be excluded from the corresponding time to event analysis (eg., FCT, etc.). Descriptive statistics will provided using the Kaplan-Meier method and Kaplan-Meier curves will be presented by treatment and cohort. For all cohorts pooled, difference for the cipargamin regimen vs artesunate will be evaluated using a log-rank test stratified by cohort. Two-sided 90% CIs for the hazard ratio will be provided.

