Fever Clearance time (FCT) (in patients with temperature of $\geq 37.5^{\circ}\text{C}$ axillary or $\geq 38.0^{\circ}\text{C}$ oral/tympanic/rectal) is defined as time from the first IV study medication until the first time the body temperature decreased below and remained below 37.5°C axillary or 38.0°C oral/tympanic/rectal for at least a further 24 hours,

Parasite clearance time (PCT) is defined as time from the first IV study medication until the first total and continued disappearance of asexual parasite forms which remained at least a further 48 hours.

Parasitaemia: P. falciparum asexual parasite counts are based on the local lab assessment for all cohorts and repeated using central lab assessments for Cohorts 1 and 2. Similar use of local lab readings and central lab readings will be applied to PRR, recrudescence, reinfection, and clinical success below.

Parasite detection limit for central lab: 0.1 parasite/uL will be used as detection limit or assay sensitivity limit for the parasite counts using the central lab.

Parasite detection limit for local lab: 10 parasite/uL will be used as detection limit or assay sensitivity limit for the parasite counts using the central lab.

PRR is defined as the ratio of asexual parasite at baseline divided by asexual parasite at post-baseline. If the asexual parasite count at post-baseline is 0, the detection limit will be used to calculate the ratio.

Recrudescence and reinfection

Recrudescence is defined as appearance of asexual parasites after clearance of initial infection with a genotype identical to that of parasites present at baseline. Recrudescence must be confirmed by PCR analysis.

Reinfection or new infection is defined as appearance of asexual parasites after clearance of initial infection with a genotype different from those parasites present at baseline.

Clinical success

Clinical success is a composite endpoint defined based on the following criteria.

A patient is said to have achieved the clinical success at a given timepoint if the patient did not die either during the initial hospitalization nor due to malaria post the initial hospitalization, shows absence of *P. falciparum* asexual parasites, and did not have any of the key signs or symptoms of severe malaria on that given timepoint.

Note: Deaths occurring post initial hospitalization will be evaluated by designated adjudication committee to confirm if they are related to malaria.

Key signs of Severe Malaria

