2.5.5 Sensitivity analyses

- After receiving antimalarial medication, a patient's parasite usually decreases log-linearly after a lag stage ([White 2011](#), [Flegg et al 2011](#)). For artemisinin derivatives, parasitaemia starts to decline in a log-linear manner almost as soon as parasitocidal drug concentrations are reached ([White 2011](#)). The Tmax is about 0.5 to 15 minutes for IV artesunate ([Artesunate PI](#)). The Tmax is about 4 hours for oral cipargamin and should be much shorter for IV cipargamin. Missing data of parasite counts at 12 hours could be well estimated using a log linear interpolation of the 2 parasite counts immediate before and after 12 hours. Since there are 3 planned parasite assessments on or after 2 hours, missing parasite count at 12 hours due to early discontinuation could be estimated using patient specific log linear regression if there are at least 2 parasite counts prior to the discontinuation. A sensitivity analysis will be performed using interpolation for missing data at intermediate time points

and extrapolation using a log linear regression if there are at least 2 parasite counts prior to discontinuation. Regression line will be fitted for each patient separately. In the event that a patient does not have at least 2 parasite counts prior to discontinuation, the patient will be imputed as not achieving $\geq 90\%$ reduction at 12 hours. Parasite counts below the limit of detection will be substituted using the limit of detection. If a patient's parasite count becomes below the limit of detection, only the first parasite count below detection will be used.

- The severity of disease is different between Cohort 1 and Cohort 2, which might impact the ability to achieve $\geq 90\%$ parasite reduction, ie., resulting in a different binomial distribution between Cohorts 1 and 2. Therefore, two-sided 90% confidence intervals (CI) for the difference between each IV cipargamin dose regimen vs IV artesunate will be provided for Cohort 1 and Cohort 2 separately, using handling of missing values not related to intercurrent events specified in [Section 2.5.4](#) and in this section.
- In order to assess the impact of IV rescue medication on parasites reduction, a listing of parasites details over time will be provided for the patients receiving IV rescue.

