- for a treatment group in a cohort with 14 patients, the probability of observing at least 2 events is about 80% if the true event rate is $\geq 20\%$ but $< 20\%$ if the true event rate is $\leq 5\%$;
- for a treatment group in a cohort with 20 patients, the probability of observing at least 3 events is about 80% if the true event rate is $\geq 20\%$ but $< 20\%$ if the true event rate is $\leq 7\%$
- for a treatment group in a cohort with 38 patients, the probability of observing at least 6 events is about 80% if the true event rate is $\geq 20\%$ but $< 20\%$ if the true event rate is $\leq 10\%$

- for a regimen that is selected for Cohorts 3-5 with 116 patients, the probability of observing at least 14 events is $> 80\%$ if the true event rate is $\geq 15\%$ but $< 20\%$ if the true event rate is $\leq 9\%$.

The minimal number of events mentioned above may be used as a guidance to interpret the occurrence of safety events in a treatment group in a cohort or pooled cohorts.

Figure 3-3 **Probability of observing selected minimal number of events by sample size**

Generated using R 3.4.3.

4 Change to protocol specified analyses

None

5 Appendix

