It has been observed in the Phase II study of oral KAE609 formulation for uncomplicated malaria that the most patients have achieved parasite clearance by 24 hours. This implies that post 24 hours results may be negative for all KAE609 patients, which results into a constant value for all the patients. For artesunate, the median parasite clearance time is expected to be >40 hours. Therefore, post 48 hours, results may be negative for all artesunate patients, which results into a constant value for all the patients. In such cases, variables with constant value will be dropped from imputation model, otherwise, SAS procedure, PROC MI will fail with error.

Clinical success at different visits will be imputed using discriminant function by FCS method. The imputations will be done separately for each treatment group. The number of imputations will be set to 100; the seed for the random function will be set to 60912201 for this study.

To generate the multiple imputed data sets, the SAS procedure MI can be used as follows:

The input data set <CLNSUC_dd> should have one record per patient with country, age, baseline weight, gender, log (parasite counts) from baseline up to 18 hours for KAE (and up to 48 hours for artesunate), parasitaemia status from 24 to 72 hours (presence/absence) for each visit for KAE609 (72 hours for artesunate), altered consciousness (yes/no) at each visit, renal impairment (yes/no) at each visit, acidosis (yes/no) at each visit, and clinical success (yes/no) at each visit.

Two outputs will be prepared displaying i) the missing data patterns and the group means as stored in the data set msgpat and ii) the variance information and estimated means with confidence interval and range based on data sets varinfo and param which need to be merged by <treatment group> and <variable>.

The imputed data are saved in data set <impdata>.

For each of the completed dataset, clinical success will be derived according the definition in [Section 2.1.1](#). The percentage of patients with clinical success (\hat{P}) at different timepoints such as 24 hours, 48 hours, 72 hours, hospital discharge, Day 6, Day 8, Day 15, Day 22, and Day 29 will be calculated as $n/N \times 100\%$ for each treatment group and for each of the complete datasets; where n =no. of patients with clinical success and N =no. of patients in FAS.

Combining clinical success rates and 90%CI for each treatment group

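### The SAP substitutes the full detection limit for zero counts in the parasite reduction ratio where the protocol uses half of it, without declaring the change, and its ANCOVA treats the substituted values as measured

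*SAP*

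**What the plan says.** **Substitution for PRR.** For a zero post-baseline count, Protocol 12.5.1 states that "the half value of detection limit will be used to calculate the ratio". SAP 2.1.1 states that "the detection limit will be used to calculate the ratio", and SAP 2.7.2.5 repeats this for counts that are "0/below assay detection limit, the detection limit will be used to calculate the ratio".

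**Substitution in the 12-hour sensitivity analysis of the primary endpoint.** Protocol 12.4.5: "Parasite counts below the limit of detection will be substituted using the half limit of detection". SAP 2.5.5: "Parasite counts below the limit of detection will be substituted using the limit of detection".

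**Declared changes.** SAP section 4, headed "Change to protocol specified analyses", contains only the word None.

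**Limits.** SAP 2.1.1 gives 10 parasites/µL for local readings (all cohorts). For the central repeat in Cohorts 1 and 2, "0.1 parasite/uL will be used as detection limit". The sentence on the local limit ends by naming the central lab, an apparent slip.

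**Model.** SAP 2.7.2.5 analyses log PRR at 12, 24 and 48 hours by ANCOVA with log baseline and treatment (plus cohort when pooled). It assumes log-normality, uses observed data and reports two-sided 90% intervals. No censored or other sensitivity analysis of PRR is planned.

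**Expected clearance.** SAP 5.8.4 reports from an oral cipargamin study in uncomplicated malaria that "most patients have achieved parasite clearance by 24 hours", and expects a median clearance time above 40 hours on artesunate. Protocol 4.2 cites mean 24-hour PRR of 7 to 43 for IV artesunate. SAP 3.1 assumes that 45% of artesunate patients reach 90% reduction at 12 hours.

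**The concern.** Two issues are joined here. The first is a plain conflict between protocol and SAP, present in two analyses and not listed as a change.

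The second matters more. For a patient whose smear is negative, PRR is no longer a measurement. It equals baseline divided by a constant that the analyst chose, and under the full-limit rule it is a lower bound. Ordinary ANCOVA enters these bounds as exact values. If one arm supplies most of them, the treatment ratio depends on the constant and the interval does not allow for what is unknown below the limit.

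The SAP handles zeros with more care elsewhere. Its clearance-rate estimator in 2.7.2.5 has a tobit branch, and the multiple imputation in 5.8.4 replaces cipargamin log counts after 18 hours by presence or absence of parasites. PRR at 24 and 48 hours gets neither. At stake is the reading of a listed secondary endpoint in the final report.

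**Working it through.** The documents state no PRR treatment ratio and no expected share of zeros, so there is no figure to reproduce.

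**1. Ceiling on PRR.** Largest attainable PRR = baseline / substituted value. At the local limit of 10: 5,000/10 = 500 and 250,000/10 = 25,000. Half the limit doubles both.

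**2. Which arm is at the floor at 24 hours.** Count = baseline / PRR. For artesunate with PRR 7 to 43:
- baseline 5,000: 5,000/7 = 714 down to 5,000/43 = 116
- baseline 50,000: 50,000/7 = 7,143 down to 50,000/43 = 1,163

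All lie well above 10, so artesunate is mostly off the floor at 24 hours, and likewise at 12 hours, where 45% with 90% reduction implies a median PRR just under 10. Most cipargamin patients are expected to be clear at 24 hours.

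**3. Effect of limit versus half-limit.** Halving the constant adds ln 2 to log PRR for each floored patient. With balanced baselines the geometric mean ratio (cipargamin/artesunate) is multiplied by 2^(fc − fa), where fc and fa are the floored fractions. The fractions below are assumed:

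| Time | fc, fa | Factor |
|---|---|---|
| 12 h | 0.30, 0 | 2^0.30 = 1.23 |
| 12 h | 0.60, 0.05 | 2^0.55 = 1.46 |
| 24 h | 0.80, 0.05 | 2^0.75 = 1.68 |
| 24 h | 0.90, 0.10 | 2^0.80 = 1.74 |
| 48 h | 0.95, 0.55 | 2^0.40 = 1.32 |
| 48 h | 1.00, 0.90 | 2^0.10 = 1.07 |

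Since fc − fa is below 1, the factor stays below 2. Where cipargamin clears more, the SAP rule gives the smaller ratio.

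**4. Shape over time.** A simulation with 38 per arm used baselines log-uniform from 5,000 to 300,000, artesunate tuned to about 42% with 90% reduction at 12 hours and 70% cleared at 48 hours, and two assumed cipargamin speeds.
- At 24 hours, 84-98% of cipargamin and 7% of artesunate were floored. The ratio was 22 to 28 with the full limit and 38 to 52 with half (factors 1.71 and 1.87).
- At 48 hours, all cipargamin and about 70% of artesunate were floored. The ratio fell to about 1.7 (full) or 2.1 (half), although the simulated underlying difference was far larger.

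**5. Bias and coverage at 24 hours.** A second simulation used 20 per arm (Cohorts 1 and 2 combined: 6 + 14), log-normal baseline (median 60,000, geometric SD 2.5, minimum 5,000), log-normal PRR with ln-SD 2.0, true ratio 300 and local limit 10. With artesunate 24-hour PRR of 20 to 40, about 50-62% of cipargamin was floored:

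| Analysis | Estimated ratio | 90% CI coverage |
|---|---|---|
| ANCOVA, full limit (SAP) | 88-121 | about 25-50% |
| ANCOVA, half-limit (protocol) | 139-182 | 59-77% |
| Left-censored normal model | 293-297 | about 89% |

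At an artesunate PRR of 7, coverage under the SAP rule is about 80%. Repeat runs move these figures by a few points.

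**6. Central readings.** Censoring the same data at 0.1, as SAP 2.1.1 implies for the central lab, gives 283-292 with about 90% coverage.

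**The case against.** The substitution rule alone has a bounded effect, cannot reverse the comparison, and in the expected scenario the SAP's version is conservative for cipargamin. PRR carries no hypothesis (SAP 2.7.2) and plays no part in the sample size. Clearance is also described by clearance time and slope half-life. The true ratio and ln-SD in the simulation are not in the documents, and the censored model was tested on data generated from its own log-normal form. All of this stands. It limits the weight of the point but leaves an undeclared conflict and an interval that treats bounds as data.

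Three stronger readings are tempting and not supported:
- **That most ratios sit at the floor.** This fits cipargamin at 24 hours and, on the assumed rates, both arms at 48 hours. It does not fit artesunate at 12 or 24 hours. Cipargamin at 12 hours is uncertain, because the evidence is oral dosing with baselines up to 60,000/µL (Protocol 4.2).
- **That the 100-fold gap between local and central limits inflates the central ratio.** Counts between 0.1 and 10 are measured values on central readings. Only a patient reading zero in both labs has a PRR 100 times larger, and step 6 suggests that the central repeat eases the problem.
- **That the paediatric dose choice is at risk.** PRR was an output for the interim assessment after Cohort 2, but alongside safety, PK and other efficacy data, and SAP 1.1 records that the DMC has already endorsed the Cohort 3 and 4 dosing.

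**Conclusion.** The protocol and SAP conflict on the substituted value, in PRR and in the 12-hour sensitivity analysis, and the change is undeclared. This rests on the text alone.

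The statistical consequence depends on how the arms clear. If cipargamin clears much earlier than artesunate, as the documents expect, the 24-hour geometric mean ratio from the planned ANCOVA is biased toward 1 and moves with the constant, and the 48-hour ratio is compressed whichever rule is used. The coverage figures (about 80% down to about 25%, against a nominal 90%) are illustrations under the stated assumptions and are not predictions.

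The primary analysis is untouched by the PRR rule, since an absent count is a responder under either document. This is worth correcting before the final analysis; it does not threaten the trial's main conclusion.

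**What to change.** - Use one substitution rule in protocol and SAP, for PRR and for the 12-hour sensitivity analysis, or list the change and its reason in SAP section 4. Correct the wording of the local-limit sentence in SAP 2.1.1 at the same time.
- Report the percentage of counts at the limit beside each PRR, by arm and time point.
- Keep the ANCOVA and add, as a sensitivity analysis, a left-censored normal (Tobit) model for the log post-baseline count with treatment and log baseline (and cohort when pooled). Enter zeros as below the limit of the lab that read the slide.
- Where nearly all counts in an arm are zero, report the proportion cleared and no ratio.

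The cost is SAP text and one standard procedure (for example PROC LIFEREG), with no new data. The censored model relies on log-normality below the limit and may not be estimable at 48 hours. It can also be thin at 24 hours: with 84-98% of cipargamin cleared, an arm of 38 has about 38 × 0.16 = 6 down to 38 × 0.02 = 1 measured counts. That is why it should stand beside the ANCOVA and not replace it.
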